#### 6.2.3.5 Month $12 \pm 6$ weeks (Visit 5)

The following procedures will be performed at 12 months after the baseline. Data will be collected from the medical charts and recorded on the CRF when they are available.

- Record the weight and alcoholic status (defined as  $\geq 8$  units of consumption per week)
- Record the active or newly onset of comorbidities since the visit 4 (during Month 9 to Month 12). Comorbidities include hypertension, diabetes, congestive heart failure, vascular disease (myocardial infarction, peripheral artery disease, and complex aortic plaque), ischemic heart disease, left ventricular dysfunction, stroke, transient ischemic attack, thromboembolism, abnormal kidney function (chronic dialysis, renal transplantation, serum creatinine ≥ 200 μmol/L, or eGFR < 60 mL/min/1.73 m²), abnormal liver function (chronic hepatic disease [e.g., cirrhosis] or biochemical evidence of significant hepatic derangement [e.g., bilirubin > 2 × upper limit of normal, in association with AST/ALT/ALP > 3 × upper limit normal]), major bleeding, and predisposition to bleeding/anemia.
- Collect the results of serum creatinine (will be used to calculate CrCl by Cockcroft-Gault formula) and eGFR if available in medical record. Only the values within the allowed window and closest to 12 months will be collected.
- To acquire HAS-BLED score:
  - Record the results of bilirubin, AST, ALT, ALP, INR and PT if available in medical record. Only the values within the allowed window and closest to 12 months will be collected.
  - Record if the subject is receiving chronic dialysis or have undergone renal transplant due to abnormal renal function, and medication usage predisposing to bleeding (antiplatelet agents or NSAIDs) during 9 to 12 months
- Record the use of dabigatran (dose, date of administration)
- Record the change of concomitant therapies for AF or stroke prevention since the last visit (generic name or name of the therapy)
- Complete the measurement of MMAS-8 score
- Record the occurrence of stroke and thromboembolic events, if any
- Record the occurrence of bleeding-related events, if any
- Do safety reporting if any dabigatran relevant ADR, fatal AEs, and pregnancies occurs

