#### 7.1.3 Covariates

Patients recruited will be evaluated for covariates at the visit of baseline. Potential confounders include demographics (age, gender, race, and educational level), VASc score, HASBLED score, comorbidities, concomitant therapies, dose of dabigatran, and renal function.

Statistical methods will be performed to test the difference of covariates between the study group at the visit of baseline (please referred to section 10. data analysis). If any significant difference occurred, linear regression will be conducted to model the relationship between dependent variable and all explanatory variables.

As for linear regression model, the primary endpoint (MMAS-8 score at 12 months) will be considered as dependent variable, and all covariates listed above including study group variable will be considered as explanatory variable.

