#### 7.1.3.5 HAS-BLED score

HAS-BLED is a scoring system developed to assess 1-year risk of major bleeding in patients with AF. The HAS-BLED score is composed of seven items with a maximum score of 9. Among all the items, 2 of them will be scored with 1 or 2 points depending on the number of corresponding description, including "abnormal renal and liver function" and "drugs or alcohol", while the other five items are counted as 1 point of each. A higher score corresponds to a greater risk of bleeding, and a score of  $\geq$  3 points indicates "high risk". The HAS-BLED score will be calculated according to Table 3.

If labile INRs in current study is not known, we will consider it as no labile INRs in calculating HAS-BLED score under the premise of no statistical significant difference in the distribution of labile INRs between two study group.

Besides labile INRs, if any of the clinical characteristic shown in Table 3 is missing or not known, the HAS-BLED score will be considered as a missing value during data analysis.

Table 3 Clinical characteristics composing the HAS-BLED score

Letter	Clinical Characteristic	Score
Н	Hypertension 	1
A	Abnormal renal function  and abnormal liver function  (1 point each)	1 or 2
S	Stroke 	1
В	Bleeding 	1

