#### 8. DATA SOURCES

As this is a NIS, no diagnostic or monitoring procedures additional to the standard of care and routine practice (except for the additional education delivered to the experimental group) will be applied to the patients. All the assessment will be performed by the investigator if they are deemed necessary for the medical treatment procedure.

This study will collect the data from medical charts and MMAS-8 questionnaires. Investigators or delegated site staffs will record the data on the CRF. Data source includes questionnaires, hospital discharge files, abstracts of primary clinical records, electronic medical records, clinical databases, administrative records such as eligibility files, prescription drug files, biological measurements, exposure/work history record reviews, etc.

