#### 9.2 Handling of Missing Values

No imputation method will be performed to estimate the missing values for all the study variables.

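### SAP 7.1.3.5 withholds HAS-BLED when any item except labile INR is unknown, even where the known items already reach 3 points, and this can drop randomised patients from the SAP 7.1.3 regression

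*SAP*

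**What the plan says.** SAP 7.1.3.5 defines the score: "The HAS-BLED score is composed of seven items with a maximum score of 9". A total of 3 or more is labelled high risk. An unknown labile INR is scored as absent, provided its distribution does not differ significantly between the groups. The next rule exempts labile INR and covers everything else: if one of the other items "is missing or not known, the HAS-BLED score will be considered as a missing value during data analysis".

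The inputs come from routine care. SAP 8 adds no tests: "All the assessment will be performed by the investigator if they are deemed necessary for the medical treatment procedure". At Month 12, SAP 6.2.3.5 says "Record the results of bilirubin, AST, ALT, ALP, INR and PT if available in medical record". Creatinine and eGFR carry the same condition, only values inside the ±6-week window count, and the other follow-up visits read alike. Baseline takes the latest earlier result, with no look-back limit (SAP 6.2.3.1).

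On missing data, SAP 9.2 states "No imputation method will be performed to estimate the missing values for all the study variables". SAP 7.1.3 lists HAS-BLED and the VASc score among the covariates. If a baseline covariate differs significantly between groups, a linear regression of the 12-month MMAS-8 score is run in which "all covariates listed above including study group variable will be considered as explanatory variable".

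**The concern.** An all-or-nothing scoring rule sits on inputs that the design expects to be incomplete. There are three consequences.

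- **Known information is discarded.** No unknown item can lower the total, so a patient already at 3 has a settled category. The SAP has no provision for this.
- **The scored patients may differ from the rest.** Tests follow the physician's judgement of need, so having a score may be related to how ill the patient looks.
- **Randomised patients can leave the adjusted comparison.** HAS-BLED is an explanatory variable and cannot be imputed, so a patient without a baseline score contributes nothing to the SAP 7.1.3 model, for a reason unrelated to adherence.

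Behind all three lies an undefined term. The liver and renal items can be met without a laboratory value (chronic hepatic disease; dialysis or transplant), and both conditions are also recorded as comorbidities. The SAP does not say whether a patient with no recorded disease and no test counts as 'no' or as 'not known'.

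**Working it through.** **1. The plan's own figure.** Table 3 weights: H 1 + A 2 + S 1 + B 1 + L 1 + E 1 + D 2 = 9, from seven items. This agrees with the SAP.

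**2. When the category is already fixed.** Setting labile INR to 0, as the SAP allows, leaves eight yes/no components: hypertension, renal, liver, stroke, bleeding, elderly, drugs, alcohol.

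| Unknown | Patterns of known components | Already ≥ 3 | Cannot reach 3 | Undetermined |
|---|---|---|---|---|
| Liver | 2^7 = 128 | 128 − (1 + 7 + 21) = 99 | 1 + 7 = 8 | 21 |
| Liver, renal | 2^6 = 64 | 64 − (1 + 6 + 15) = 42 | 1 | 6 + 15 = 21 |
| Liver, renal, hypertension | 2^5 = 32 | 32 − (1 + 5 + 10) = 16 | 0 | 16 |

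These are pattern counts, not patient frequencies. The SAP makes every pattern missing.

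Example: aged 70 (1), prior stroke (1), on an antiplatelet (1), anemia (1), liver status not known. The known total is 4 and the true total 4 or 5 (labile INR at 0). The recorded score is missing.

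**3. How loss accumulates.** The documents give no missingness rate. If each of k items is unknown independently with probability m, the share with no score is 1 − (1 − m)^k. For m = 10%, 20% and 30% (assumed), two items give 19%, 36% and 51%.

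**4. Direction of selection.** Let p be the true high-risk share, and a and b the missing shares in high-risk and other patients. The observed share is p(1 − a) / [p(1 − a) + (1 − p)(1 − b)]. With p = 20% (assumed):

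- a = 10%, b = 40%: 0.18 / (0.18 + 0.48) = 27.3%
- a = 40%, b = 10%: 0.12 / (0.12 + 0.72) = 14.3%
- a = b: 20%

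**5. Illustrative size at one follow-up visit.** Assumptions, none from the documents: independent items with prevalences liver 3%, renal 1%, stroke 8%, bleeding 8%, elderly 45%, drugs 25%, alcohol 12%, hypertension item 6%; only the liver item depends on labs; labs available for 30–70% overall; odds of having labs multiplied by 1 to 3 when known items total 2 or more. I use 1,200 × 0.80 = 960 patients (the plan's target is 1,000).

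- Exact enumeration gives 6.1% truly at 3 or more, and 5.48% at 3 or more on known items alone: 960 × 0.0548 = 52.6 patients.
- Of these, the number set to missing is 52.6 × (1 − availability among them). At odds ratio 1 this is 52.6 × 0.7 = 37 (30% available) or 52.6 × 0.3 = 16 (70% available). At odds ratio 3 with 70% available overall, their availability is 84.4%, giving 8.
- The observed share at 3 or more is 6.1–9.8%. With odds ratios of 1/3 to 1/2 instead, it is 3.2–5.2%.
- The extremes come from different scenarios: 37 arises where there is no bias, and 9.8% goes with about 28 patients set to missing.

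**6. The regression.** If a share m lacks a baseline score (10–30% assumed), 960 × (1 − m) = 864 to 672 remain. The standard error rises by 1/√(1 − m): 1/√0.9 = 1.05 to 1/√0.7 = 1.20, with the residual variance unchanged.

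**The case against.** The strongest reply is that the data loss is not established. The SAP never says that an absent lab makes an item 'not known', and a programmer could score the item from the comorbidity record and lose few patients. That stands: the documents show an undefined term and a rule that is wrong when it applies, not a number of lost scores.

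A reader might also infer more than the text supports:

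- *Any single unknown item voids the score.* Labile INR is expressly exempt.
- *Follow-up bleeding risk will be overstated.* Need-driven testing makes that plausible, but step 4 gives either direction.
- *High-risk patients vanish from a planned count.* No such count is visible. HAS-BLED is not a listed primary or secondary outcome, the paired tests in SAP 10 name no variable, and some SAP pages show no text.
- *Baseline is as exposed as follow-up.* It is not. There is no look-back limit, and the Ccr < 30 mL/min exclusion in practice needs a creatinine, so the exposure is mainly liver tests.

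It is also fair to say that the rule is prespecified, matches the one for the VASc score (SAP 7.1.3.4), that SAP 10 will report missing numbers, and that Protocol 9.9 names absent chart data as a limitation. None of this repairs a category that is known and then discarded, or keeps a randomised patient in the model.

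**Conclusion.** The point holds in a limited form. When an item other than labile INR is treated as unknown, the SAP withholds a score even if the known items already total 3 or more. This follows from the scoring alone and needs no assumption about rates. Scored patients may be a selected subset, but the size and direction of any bias cannot be learned from the documents. The 8–37 patients per 960 and the observed shares in the working are illustrations on assumed inputs.

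The SAP 7.1.3 regression loses any randomised patient without a baseline score, but only if a significant baseline difference triggers it. The 5–20% rise in standard error rests on an assumed 10–30% missing at baseline. The primary chi-square or Fisher comparison does not use HAS-BLED and is unaffected, so this is worth correcting but does not threaten the main result.

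A related gap: the hypertension item requires systolic pressure above 160 mmHg (Table 3, note 1), yet Table 1 lists no blood pressure. Read literally, that item could void scores too.

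**What to change.** - **SAP 7.1.3.5, item definitions.** Score the liver and renal items from the recorded comorbidity and therapy data plus any available lab, and state when an item is 'no' and when it is 'not known'. For the renal item use its components: the comorbidity field also counts eGFR < 60 (SAP 7.1.3.2), which Table 3 does not, so a 'yes' there need not score a point. Do not carry labs forward unless that is also declared an exception to SAP 9.2.
- **SAP 7.1.3.5, category.** Wherever HAS-BLED of 3 or more is reported, classify a patient as 3 or more when the known items already reach it. Otherwise give the lowest and highest possible shares. In those bounds, treat an item with no lab as unknown even if the main scoring sets it to 'no'; otherwise the bounds cannot show the effect of an untested abnormality.
- **SAP 7.1.3, model.** Keep patients with a missing baseline HAS-BLED or VASc score by a missing-indicator or the overall mean, declared as an exception to SAP 9.2 for baseline covariates only.
- **Hypertension item.** Reconcile Table 3, note 1, with Table 1.

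Cost: SAP wording, slightly more programming and a declared exception to the no-imputation rule. The scoring and model changes need no new data; whether the hypertension item does depends on how that text is reconciled. Protocol 9.7.3 already permits imputation described in the SAP.

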## Statistical Analysis Plan (SAP) for Non-Interventional Studies (NIS) BI Study Number 1160-0304

Page 22 of 27

L	Labile INRs 	1
Е	Elderly, age > 65 years	1
D	Drugs or alcohol (1 point each) 	1 or 2

- 1. Hypertension should be uncontrolled, with systolic blood pressure > 160 mmHg.
- 2. Abnormal kidney function is classified as a presence of chronic dialysis, renal transplantation, or serum creatinine  $\geq 200 \ \mu mol/L$ .
- 3. Abnormal liver function is defined as the chronic hepatic disease (e.g., cirrhosis) or biochemical evidence of significant hepatic derangement (e.g., bilirubin > 2 × upper limit of normal, in association with AST/ALT/ALP > 3 × upper limit normal, and so forth.)
- 4. Previous history, particularly lacunar.
- 5. Bleeding history, such as prior major bleeding or predisposition to bleeding (e.g., anemia).
- 6. Labile INR (e.g., therapeutic time in range < 60%).
- 7. Drugs are medication usage predisposing to bleeding (e.g. antiplatelet agents or NSAIDs). Ethanol abuse is classified as  $\geq 8$  units of alcoholic consumption per week.

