 - Currently ongoing diseases: Hypertension, diabetes, congestive heart failure, left ventricular dysfunction, abnormal kidney function (chronic dialysis, renal transplantation, serum creatinine ≥ 200 μmol/L, or eGFR < 60 mL/min/1.73 m²), abnormal liver function (chronic hepatic disease [e.g., cirrhosis] or biochemical evidence of significant hepatic derangement [e.g., bilirubin > 2 × upper limit of normal, in association with AST/ALT/ALP > 3 × upper limit normal]), major bleeding, and predisposition to bleeding/anemia.
 - Prior events: Vascular disease (myocardial infarction, peripheral artery disease, and complex aortic plaque) ischemic heart disease, stroke, transient ischemic attack, and thromboembolism
- 4. At follow-up visits, only the current and newly onset of comorbidities since the last visit should be recorded. Comorbidities include hypertension, diabetes, congestive heart failure, vascular disease (myocardial infarction, peripheral artery disease, and complex aortic plaque), ischemic heart disease, left ventricular dysfunction, stroke, transient ischemic attack, thromboembolism, abnormal kidney function (chronic dialysis, renal transplantation, serum creatinine ≥ 200 μmol/L, or eGFR < 60 mL/min/1.73 m²), abnormal liver function (chronic hepatic disease [e.g., cirrhosis] or biochemical evidence of significant hepatic derangement [e.g., bilirubin > 2 × upper limit of normal, in association with AST/ALT/ALP > 3 × upper limit normal]), major bleeding, and predisposition to bleeding/anemia
- 5. CrCl will be calculated using Cockcroft-Gault formula.
 - For baseline, the most updated results prior to the enrolment will be collected.
 - For follow-up visits, data within the allowed window and closest to the visit will be collected.
- 6. Lab data include liver function tests (bilirubin, aspartate aminotransferase [AST], alanine aminotransferase [ALT], and alkaline phosphatase [ALP]) and coagulation tests

NIS Protocol Page 20 of 46

(international normalized ratio [INR] and prothrombin time [PT]. For baseline, the most updated results prior to the enrolment will be collected.

- For follow-up visits, data within the allowed window and closest to the visit will be collected.
- 7. Concomitant therapies are chronic dialysis or renal transplant due to abnormal renal function & medication usage predisposing to bleeding (antiplatelet agents or nonsteroidal anti-inflammatory drugs [NSAIDs]).

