9.2.3.1 Screening/Baseline (Visit 1)

The following procedures will be performed at the baseline visit. Data will be collected from the medical charts and recorded on the CRF when they are available.

- Collect signed informed consent form. A copy of the signed consent should be given to the patient.
- Assess the eligibility according to the inclusion/exclusion criteria and record the date of inclusion
- Randomize the eligible patients into one of the study groups (standard of care OR standard of care with advanced educational intervention)
- Collect demographic data (date of birth, gender, race, education level, height, weight, and alcoholic status [defined as ≥ 8 units of consumption per week])
- Record AF-related medical histories
- Record the following comorbidities:
 - Currently ongoing diseases: Hypertension, diabetes, congestive heart failure, left ventricular dysfunction, abnormal kidney function (chronic dialysis, renal

NIS Protocol Page 21 of 46

transplantation, serum creatinine $\geq 200~\mu mol/L$, or eGFR < 60 mL/min/1.73 m²), abnormal liver function (chronic hepatic disease [e.g., cirrhosis] or biochemical evidence of significant hepatic derangement [e.g., bilirubin > 2 × upper limit of normal, in association with AST/ALT/ALP > 3 × upper limit normal]), major bleeding, and predisposition to bleeding/anemia.

- Prior events: Vascular disease (myocardial infarction, peripheral artery disease, and complex aortic plaque), ischemic heart disease, stroke, transient ischemic attack, and thromboembolism
- Collect the latest results of serum creatinine (will be used to calculate CrCl by Cockcroft-Gault formula) and eGFR prior to the baseline
- To acquire HAS-BLED score:
 - Record the latest results of bilirubin, AST, ALT, ALP, INR, and PT prior to the baseline
 - Record if the subject is receiving chronic dialysis or had undergone renal transplant due to abnormal renal function prior to the baseline; and medication usage predisposing to bleeding (antiplatelet agents or NSAIDs) within 1 month prior to the baseline
- The educator delivers advanced education to subjects in the experimental group.
- Record the use of dabigatran (dose, date of administration)
- Record the concomitant therapies for AF or stroke prevention within 1 month prior to the baseline (generic name or name of the therapy)
- Record the occurrence of stroke and thromboembolic events, if any
- Record the occurrence of bleeding-related events, if any

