#### 6.2.3 STUDY VISITS

The collection of patient data will be managed in line with routine clinical practice in an outpatient manner, which will have follow-ups at approximately every 3 months in Taiwan. Information on variables of interest will be collected at inclusion (baseline visit) and captured during the follow-up period at 3, 6, 9, and 12 months (time window:  $\pm$  6 weeks) until completion of the study.

Data will be collected and recorded on the CRF according to Table 1 which lists all of the data of interests with an "X" to show the time points when they are collected. Data will be collected after the patient has consented to participate in the study. Once the patient has signed the informed consent form, the patient is considered to be enrolled in the study and patient details should be recorded on the enrolment log.

Table 1 Data collection schedule

Event	Screening/Baseline	Follow-up			
Visit	1	2	3	4	5
Month	0	3	6	9	12
Week	0	12	24	36	48
Allowed window	==		± 6 v	veeks	
Informed consent	X	·			
Inclusion/exclusion	X				
Randomization	X				
Demographics 	X	W/A	W/A	W/A	W/A
AF-related medical histories 	X				
Comorbidities	$X^3$	$X^4$	$X^4$	$X^4$	$X^4$
Serum creatinine (for CrCl) and eGFR 	X	X	X	X	X
VASc score	X	X	X	X	X
HAS-BLED score	X	X	X	X	X
Lab data for HAS-BLED 	X	X	X	X	X
Concomitant therapies for HAS-BLED 	X	X	X	X	X
Education (experimental group)	X	X	X	X	
Dabigatran treatment	X	X	X	X	X
Concomitant therapies for AF or stroke 	X	X	X	X	X
MMAS-8 score		X	X	X	X
Stroke and thromboembolic events 					→
Bleeding-related events 					→
Safety reporting 					$\rightarrow$

- Demographics include date of birth, gender, race, education level, height, weight, and alcoholic status (defined as ≥ 8 units [1 unit = approximately 355-mL beer, 150-mL wine, 20-mL Kaoliang] of consumption per week). Follow-up visits will only collect weight (W) and alcoholic status (A).
- 2. Include date of AF diagnosis and type of AF (paroxysmal, persistent or permanent).

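### HAS-BLED item H needs a systolic pressure above 160 mmHg, but no blood pressure or control-status field is scheduled, so in patients with hypertension H cannot be derived or checked from the planned data

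*SAP*

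**What the plan says.** Protocol 9.3.3.5 and SAP 7.1.3.5 use the same Table 3. Footnote 1 limits item H: "Hypertension should be uncontrolled, with systolic blood pressure > 160 mmHg".

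The SAP section adds two rules for missing items. One exempts labile INR: "If labile INRs in current study is not known, we will consider it as no labile INRs", provided its distribution does not differ significantly between the groups. The other covers every other item: if one "is missing or not known, the HAS-BLED score will be considered as a missing value during data analysis". SAP 9.2 rules out imputation for all study variables.

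The text introducing Table 1 (protocol 9.2.3, SAP 6.2.3) says that the table "lists all of the data of interests with an" X at each time point. It has no row for blood pressure or vital signs. Footnote 1 to Table 1 gives the personal measures: "Demographics include date of birth, gender, race, education level, height, weight, and alcoholic status". Only weight and alcohol status are repeated at follow-up. Hypertension appears among the comorbidities, from the medical record: "Currently ongoing diseases: Hypertension, diabetes, congestive heart failure, left ventricular dysfunction". No pressure value or control status goes with it.

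Each of the five visits has a list of what to record for HAS-BLED. At baseline it starts: "Record the latest results of bilirubin, AST, ALT, ALP, INR, and PT prior to the baseline". It then adds dialysis or transplant and drugs that predispose to bleeding. The follow-up lists have the same content.

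HAS-BLED is scheduled at all five visits. It is also a covariate in SAP 7.1.3, where, if a baseline difference between groups is significant, a linear regression of the 12-month MMAS-8 score is run and "all covariates listed above including study group variable will be considered as explanatory variable".

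**The concern.** The plan defines an item by a measurement that it does not schedule, and then voids the whole score when an item is unknown. Someone deriving HAS-BLED from the listed fields must either leave H unknown in hypertensive patients, and lose their scores, or score H from the comorbidity tick, which contradicts Table 3 and can only raise the score.

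Two uses are exposed: the description of bleeding risk at each visit, and the only covariate-adjusted comparison of the groups in the SAP. In that model the loss is selective, because it falls on patients with one named comorbidity.

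**Working it through.** **Step 1. Match each Table 3 item to a scheduled field.**

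| Item | Scheduled source |
|---|---|
| H, systolic > 160 mmHg | none; comorbidity tick only |
| A, renal | serum creatinine, dialysis, transplant |
| A, liver | bilirubin, AST, ALT, ALP, chronic hepatic disease |
| S, stroke | comorbidities, prior events |
| B, bleeding | comorbidities: major bleeding, predisposition/anemia |
| L, labile INR | INR; unknown treated as not labile (conditional) |
| E, age > 65 | date of birth |
| D, drugs / alcohol | antiplatelets and NSAIDs / alcohol status |

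The points add up to the stated maximum: 1 + 2 + 1 + 1 + 1 + 1 + 2 = 9. H is the one item with neither a usable input nor an exemption.

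**Step 2. Apply the SAP rules to the scheduled fields.** Let N be the planned analysis number (1,000, protocol 9.1 and SAP 6.1), h the share with recorded hypertension, and u the share of those with systolic pressure above 160 mmHg. The documents give neither h nor u. I assume h = 40 to 80% and u = 5 to 20%.

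- Strictest reading (H unknown for everyone): missing = N = 1,000 of 1,000.
- No recorded hypertension counts as H = 0: missing = N × h.
- Comorbidity tick used as H: patients scored one point too high = N × h × (1 − u); excess in the mean score = h × (1 − u).

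| h | Missing, N × h | Over-scored, u = 20% | Over-scored, u = 5% | Excess in mean score |
|---|---|---|---|---|
| 40% | 400 | 320 | 380 | 0.32 to 0.38 |
| 60% | 600 | 480 | 570 | 0.48 to 0.57 |
| 80% | 800 | 640 | 760 | 0.64 to 0.76 |

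**Step 3. Effect on the SAP 7.1.3 regression.** With no imputation, a patient without a score drops out of a model that includes it. If H = 0 is allowed for patients without hypertension, 1,000 − 400 = 600 down to 1,000 − 800 = 200 patients remain. With the same residual variance, the standard error of the group effect grows by √(1,000/600) = 1.29 to √(1,000/200) = 2.24. All remaining patients are non-hypertensive, so the hypertension covariate is constant and the estimate applies only to that subset. On the strictest reading no complete record remains.

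**Step 4. Third route.** If the site reads the pressure in the chart and scores H itself, the missing and over-scored counts in Step 2 do not arise. The database then holds a score, but no field against which H can be checked.

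**The case against.** A reader might infer that the score must be missing for every patient, or else inflated. The documents do not force that choice. HAS-BLED score is a row of its own in Table 1, separate from its laboratory and therapy rows, and both documents say that it is recorded at each visit. Charts are a data source, and protocol 9.8 mentions physical examination among the data kept on the CRF. A site could therefore apply the 160 mmHg criterion without a separate field, and neither document says whether the site or the CRO scores H. A patient with no recorded hypertension can also reasonably be scored H = 0, although the SAP does not say so. Both points stand.

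A reader might also infer that the proportion at high risk (3 points or more) would be overstated by a known factor. The documents give no prevalences from which to calculate one, and the visible text labels that range without planning an analysis of it.

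The HAS-BLED lists also omit age, alcohol, stroke and bleeding history, so absence from them proves little alone. That is fair, but those inputs are scheduled elsewhere and blood pressure is not. The sentence in protocol 9.8 is a general quality-control statement and schedules nothing.

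Finally, HAS-BLED is not in the objectives or in the listed primary and secondary outcomes, and the regression is conditional. This limits the importance of the point without removing it.

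**Conclusion.** The gap is real and should be closed before analysis. Its consequence depends on a choice that the plan leaves open:

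- **Derived from scheduled fields under SAP 7.1.3.5:** missing for at least every patient with recorded hypertension, and for everyone on the strictest reading. The regression, if triggered, loses those patients.
- **Comorbidity tick used for H:** one point too many for every hypertensive patient at or below 160 mmHg. The direction is certain; the amount cannot be fixed from the documents.
- **Scored by the site from charted pressure:** neither missing nor inflated for this reason, but H cannot be verified from the database.

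The counts above rest on the assumed h and u. The primary comparison of high adherence at 12 months (chi-square or Fisher's exact test) does not use HAS-BLED and is unaffected. The point therefore concerns the bleeding-risk description and the conditional adjusted model only.

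**What to change.** 1. Add the charted systolic pressure to Table 1 and to the HAS-BLED list at each visit, with the rule used for the laboratory data: the latest value before baseline, then the value within the window and closest to the visit.
2. In SAP 7.1.3.5 state that H = 1 only if hypertension is recorded and that pressure is > 160 mmHg; that H = 0 if no hypertension is recorded or the pressure is ≤ 160 mmHg; and that the comorbidity alone does not score H. State who assigns H.
3. Where H remains unknown, report a score without H, labelled as such (maximum 9 − 1 = 8), and use that version for all patients in the regression, so that no one is dropped for this reason.
4. Reconcile this with the protocol abstract, which names a modified HAS-BLED for newly initiated patients that is never defined.

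The cost is one CRF field per visit from routine charts, with no added procedure, and a few sentences in the SAP. If collection has closed, the value can be extracted from the charts. The downside is that some visits will have no charted pressure; item 3 covers those, at the price of a score that is not the full HAS-BLED.
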